**Table 3. Study Drug Dose Modification Guidance**

Dose Level	Selinexor	Clarithromycin	Pomalidomide	Dexamethasone
0	60 mg on days 1, 8 and 15	500 mg twice daily	4 mg daily on days 1-21	40 mg on days 1, 8, 15 and 22
-1	40 mg on days 1, 8 and 15	500 mg once daily	3 mg daily on days 1-21	20 mg on days 1, 8, 15 and 22
-2	20 mg on days 1, 8 and 15	250 mg once daily	2 mg daily on days 1-21	20 mg on days 1 and 15

**Table 4. Supportive Care and Dose Adjustment Guidelines**

Toxicity	Grade	Dose Modification
Selinexor		

Fatigue	Grade 1 or Grade 2 lasting $\leq$ 7 days	
Maintain dose. Rule out other causes of fatigue, particularly dehydration and anemia. If found to be anemic, consider transfusing for Hb <math><</math> 8 g/dL.
 
Institute supportive care medications per institutional guidelines. Consistent with the National Comprehensive Cancer Network (NCCN) Clinical Practice Guidelines in Oncology (CPGO), the use of methylphenidate should be considered. Additional options are provided in the NCCN CPGO.
 
Patients with significant fatigue after several doses of selinexor may have an ongoing anti-tumor response. If fatigue is significant, consider assessment of tumor response as part of the patient's evaluation.

	Grade 2 lasting $>$ 7 days or Grade 3	
Interrupt selinexor dosing. Monitor until fatigue resolves to Grade 1 or baseline and restart selinexor at 1 dose level lower.
 
Institute supportive care medications as described above for Grade 1 or 2.
 
Patients with significant fatigue after several doses of selinexor may have an ongoing anti-tumor response. If fatigue is significant, consider assessment of tumor response as part of the patient's evaluation.

Anorexia or Weight Loss	Grade 1	
Maintain dose. Rule out other causes of anorexia. Nutritional consultation can be helpful.
 
Consider instituting supportive care medications per institutional guidelines.
 
Consistent with the NCCN CPGO, megestrol acetate 200-400 mg twice daily should be considered. Other options are provided in the NCCN CPGO.

	Grade 2	
Rule out other causes of anorexia and order a nutritional consultation.
 
Institute supportive care medications as described for Grade 1 anorexia or weight loss above. For additional options, see NCCN CPGO.
 
Interrupt dosing with selinexor until improves to Grade 1 or baseline and weight stabilizes, then restart selinexor at 1 dose level lower.

	Grade 3	
Nutritional consultation and supportive care medications for anorexia per institutional guidelines should already be instituted. For additional options, see NCCN CPGO.
 
Interrupt dosing with selinexor until improves to Grade 1 or baseline and the weight stabilizes. Restart selinexor at 1 dose level reduction.

Nausea and/or Vomiting	Grade 1 or 2	
Maintain dose. Rule out other causes of nausea.
 
Patients should be receiving 5HT3 antagonists unless contra-indicated. For those patients who cannot receive 5HT3 antagonists, consider olanzapine per NCCN CPGO. For additional options, see NCCN CPGO.

		If intolerable or persistent Grade 2, follow guidelines for Grade 3.
Hyponatremia	Grade 3	
Supportive care medications per institutional guidelines should already be instituted. For additional options, see NCCN CPGO.
 
Interrupt selinexor dosing until resolved to Grade <math>\leq</math> 2 or baseline. Restart selinexor at 1 dose level lower.
 
If nausea stabilizes for at least 4 weeks at Grade <math>\leq</math> 1, may re-escalate to the original dose after consulting Medical Monitor.

	Grade 1	
Maintain dose. Rule out other causes including drug (e.g., diuretic) effects. Be certain that reported sodium level is corrected for concurrent hyperglycemia (serum glucose <math>> 150</math> mmol/L).
 
Treat hyponatremia per institutional guidelines including dietary review. Consider addition of salt tablets to patient's diet.

	Grade 2	
Correct for hyperglycemia as outlined under Grade 1.
 
Treat hyponatremia per institutional guidelines. If (corrected) sodium is Grade <math>\leq</math> 3 and continues to be asymptomatic, then patient may continue current dosing provided that intravenous saline and/or salt tablets (1-3 times daily) are provided.
 
If Grade 2 is persistent or worsens or does not respond to treatment, dose interruptions may be considered after consulting with the Medical Monitor.

	Grade 3 or 4	
Treat per institutional guidelines. Delay selinexor until sodium resolved to Grade <math>\leq</math> 1 (<math>\geq 130</math> mmol/L) then reduce selinexor dose by 1 level. If serum sodium stabilizes to Grade <math>\leq</math> 1 for at least 4 weeks, may re-escalate to previous dose of selinexor.

Diarrhea	Grade 1 or 2	
Initiate treatment for any Grade 1 diarrhea. Treat per institutional guidelines with antidiarrheals and maintain dosing.
 
For persistent Grade 2 only that does not respond to anti-diarrheals within 3 days, interrupt selinexor dosing until resolved to Grade 1, then restart at the current dose level.

	Grade 3 or 4	
Delay selinexor until resolved to Grade 1, then reduce selinexor dose by 1 dose level.
 
If diarrhea stabilizes for at least 4 weeks at Grade <math>\leq</math> 1, may re-escalate to previous dose of selinexor after consulting with the Medical Monitor.

Thrombocytopenia	Grade 1	Maintain dose.
	Grade 2 or 3 without bleeding	
Consider platelet growth factors, e.g., romiplostim, which may take up to four weeks for an effect.
 
Reduce selinexor at 1 dose level lower.
 
Patients with stable platelet counts for <math>\geq</math> 4 weeks following dose reduction may have their dose of selinexor increased by one dose level.

	Grade 4 without bleeding	Strongly consider platelet growth factors and transfuse per clinical practice/institutional guidelines. Delay dosing until recovery to $\leq$ Grade 2 or baseline and resume selinexor at 1 dose level lower.
	Grade 2 or 3 with bleeding	Delay dosing until the bleeding has stopped and the patient is clinically stable. Reduce selinexor at 1 dose level lower.
Neutropenia	Grade 3 or 4 Neutropenia without fever	Institute colony stimulating factors, and delay dosing with selinexor until ANC returns to Grade $\leq$ 2. Reduce selinexor by 1 dose level. After stabilization for at least 4 weeks, a re-escalation may be considered after discussing with the Medical Monitor.
	Grade 3 or 4 Neutropenia with fever	Institute colony stimulating factors, and delay dosing with selinexor until the patient's ANC returns to Grade $\leq$ 2 or baseline, fever has resolved, and patient's condition is stable. Reduce selinexor by 1 dose level.
Anemia	Grade 3	Treat per institutional guidelines including blood transfusions and/or erythropoietins. Consider transfusing for Hb $<$ 8 g/dL. Reduce selinexor by 1 dose level.
	Grade 4	Treat per institutional guidelines including blood transfusions and/or erythropoietins. Consider transfusing for Hb $<$ 8 g/dL. Delay dosing of selinexor until Hb is 8 g/dL or higher. Reduce selinexor by 1 dose level.
Ocular Toxicity	Grade 2, excluding cataract	Perform ophthalmologic evaluation. Interrupt selinexor and provide supportive care. Monitor until ocular symptoms resolve to Grade 1 or baseline. Restart selinexor at 1 dose level lower.
	Grade 3 or 4, excluding cataract	Permanently discontinue selinexor. Perform ophthalmologic evaluation.
Other Selinexor-related AEs	Grade 1 or 2	Maintain dose. Initiate standard supportive care per institutional guidelines.
	Grade 3	Delay dosing with selinexor until recovery to Grade $\leq$ 2 or baseline and resume selinexor at 1 dose level lower. Re-escalation can be considered after $\geq$ 4 weeks at the lower dose with reduction of the AE to Grade 1 or baseline.
	Grade 4	Delay dosing until resolved to Grade $\leq$ 2 or baseline, then resume at 1 dose level lower. If further dose reduction/interruption is desired, consultation with the Medical Monitor is required.
Clarithromycin		
Nausea and/or Vomiting	Grade 1 or 2	Maintain dose. Rule out other causes of nausea. Patients should be receiving 5HT3 antagonists unless contra-indicated. For those patients who cannot receive 5HT3 antagonists, consider olanzapine per NCCN CPGO. For additional options, see NCCN CPGO.

		If intolerable or persistent Grade 2, follow guidelines for Grade 3.
	Grade $\geq 3$	
Supportive care medications per institutional guidelines should already be instituted. For additional options see NCCN CPGO.
 
If AE is thought to be due to clarithromycin, interrupt clarithromycin dosing until resolved to Grade <math>\leq 2</math> or baseline. For first occurrence of Grade 3, if adequate supportive care resulted in an improvement to Grade 1 or baseline within 3 days, restart clarithromycin at current dose.
 
Otherwise (i.e., the recovery took longer than 3 days), restart clarithromycin at 1 dose level lower.
 
If nausea stabilizes for at least 4 weeks at Grade <math>\leq 1</math>, may re-escalate to the original dose after consulting Medical Monitor.

Other Clarithromycin-related Non-hematologic AEs	Grade $\geq 3$	Hold (interrupt) clarithromycin and follow weekly. If toxicity has resolved to Grade $\leq 1$ , restart clarithromycin at next lower dose level.
Dexamethasone		
Dyspepsia, Gastritis, Gastric or Duodenal Ulcer	Grade $\geq 3$	Hold (interrupt) dexamethasone and follow weekly. If toxicity has resolved to Grade $\leq 1$ , restart dexamethasone at next lower dose level.
Edema	Grade $\geq 3$	Reduce the dose of dexamethasone by 1 dose level. Use diuretics as needed.
Agitation, Confusion, and/or other Psychiatric Disorder	Grade $\geq 2$	Hold (interrupt) dexamethasone and follow weekly. If toxicity has resolved to Grade $\leq 1$ , restart dexamethasone at next lower dose level.
Generalized Muscle Weakness	Grade $\geq 3$	Reduce the dose of dexamethasone by 1 dose level, if symptoms persist, continue to reduce the dose of dexamethasone by 1 dose level as needed until toxicity has resolved to Grade $\leq 2$ .
Hyperglycemia	Grade $\geq 3$	Reduce the dose of dexamethasone by 1 dose level. Start insulin or other hypoglycemic therapy as needed.
Acute Pancreatitis	Grade $\geq 3$	Discontinue dexamethasone. Remove patient from study.
Other Dexamethasone-related Non-hematologic AEs	Grade $\geq 3$	Hold (interrupt) dexamethasone and follow weekly. If toxicity has resolved to Grade $\leq 1$ , restart dexamethasone at next lower dose level.
Pomalidomide		
	Onset day 1-14 of cycle	Onset <math>\geq</math> day 15 of cycle

	Grade 3 without fever	Maintain dose.	Maintain dose.
Neutropenia	Grade 3 with fever or Grade 4	Hold (interrupt) pomalidomide and follow CBC weekly. If neutropenia has resolved to Grade $\leq$ 2 prior to day 21, restart pomalidomide at next lower dose level and continue the cycle through day 21. If neutropenia is the only toxicity for which a dose reduction is required, G-CSF may be used and the pomalidomide dose maintained.	Omit pomalidomide for the remainder of cycle. See instructions for initiation of a new cycle and reduce the dose of pomalidomide by 1 dose level. If neutropenia is the only toxicity for which a dose reduction is required, G-CSF may be used and the pomalidomide dose maintained for the next cycle at the Investigators discretion.
	Grade 1 or 2	Maintain dose.	Maintain dose.
Thrombocytopenia	Grade 3 or 4	Hold (interrupt) pomalidomide and follow CBC weekly. If thrombocytopenia has resolved to Grade $\leq$ 2 prior to day 21, restart pomalidomide at next lower dose level and continue the cycle through day 21.	Omit pomalidomide for the remainder of cycle. See instructions for initiation of a new cycle and reduce the dose of pomalidomide by 1 dose level.
Non-blistering rash	Grade 3	Hold (interrupt) pomalidomide and follow weekly. If toxicity has resolved to Grade $\leq$ 1 prior to day 21, restart pomalidomide at next lower dose level and continue the cycle through day 21.	Omit pomalidomide for the remainder of cycle. See instructions for initiation of a new cycle and reduce the dose of pomalidomide by 1 dose level.
	Grade 4	Discontinue pomalidomide. Remove patient from study.	Discontinue pomalidomide. Remove patient from study.
Desquamating (blistering) rash	Any grade	Discontinue pomalidomide. Remove patient from study.	Discontinue pomalidomide. Remove patient from study.
Neuropathy	Grade 3	Hold (interrupt) pomalidomide and follow weekly. If toxicity has resolved to Grade $\leq$ 1 prior to day 21, restart pomalidomide at next lower	Omit pomalidomide for the remainder of cycle. See instructions for initiation of a new cycle and reduce the dose of pomalidomide by 1 dose level.

		dose level and continue the cycle through day 21.	
	Grade 4	Discontinue pomalidomide. Remove patient from study.	Discontinue pomalidomide. Remove patient from study.
Thromboembolic event	Grade 3 or 4	Hold (interrupt) pomalidomide and start therapeutic dose anticoagulation. Restart pomalidomide at the Investigator's discretion maintaining dose level.	Omit pomalidomide for the remainder of cycle and start therapeutic dose anticoagulation.
Hyperthyroidism	Grade 3 or 4	Omit pomalidomide for the remainder of the cycle, evaluate etiology and initiate appropriate therapy. See instructions for initiation of a new cycle and reduce the dose of pomalidomide by 1 dose level.	Omit pomalidomide for the remainder of the cycle, evaluate etiology and initiate appropriate therapy. See instructions for initiation of a new cycle and reduce the dose of pomalidomide by 1 dose level.
Hypothyroidism	Grade 3 or 4	Omit pomalidomide for the remainder of the cycle, evaluate etiology and initiate appropriate therapy. See instructions for initiation of a new cycle and reduce the dose of pomalidomide by 1 dose level.	Omit pomalidomide for the remainder of the cycle, evaluate etiology and initiate appropriate therapy. See instructions for initiation of a new cycle and reduce the dose of pomalidomide by 1 dose level.
Other Pomalidomide-related non-hematologic AEs	Grade 1 or 2	Maintain dose. Initiate standard supportive care per institutional guidelines.	Maintain dose. Initiate standard supportive care per institutional guidelines.
	Grade 3 or 4	Hold (interrupt) pomalidomide and follow weekly. If toxicity has resolved to Grade $\leq 2$ prior to day 21, restart pomalidomide at next lower dose level and continue the cycle through day 21.	Omit pomalidomide for the remainder of the cycle. See instructions for initiation of a new cycle and reduce the dose of pomalidomide by 1 dose level.

All dose modifications should be based on the worst preceding toxicity.

**Note:** For combinations of Grade 1 or 2 AEs (e.g., nausea, fatigue, anorexia) that significantly impair the patient's quality of life, 1-2 doses of selinexor may be skipped and aggressive supportive care implemented. Selinexor may then be restarted at the original dose.

National Comprehensive Cancer Network. NCCN Clinical Practice Guidelines in Oncology (NCCN Guidelines): Fatigue, Palliative Care, and Antiemesis. Available at [http://www.nccn.org/professionals/physician\\_gls/f\\_guidelines.asp](http://www.nccn.org/professionals/physician_gls/f_guidelines.asp).

Isolated values of  $\geq$  Grade 3 alkaline phosphatase do NOT require dose interruption. Determination of liver versus bone etiology should be made, and evaluation of gamma-glutamyl transferase, 5'-nucleotidase, or other liver enzymes should be performed.

The possibility of overlapping toxicities with selinexor, pomalidomide, and dexamethasone should be considered.

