#### **7.7.1 Dosing Delays/Dose Modifications**

In order to optimize specific anti-tumor activity and tolerability, dose reductions and/or schedule modifications will be allowed. Patients should also be treated aggressively with supportive care to reduce toxicities. Doses must be adjusted for adverse events deemed related to study drug by the Investigator. Doses may be adjusted for adverse events related to study medications not listed below at the discretion of the Investigator.

Toxicity will be graded according to CTCAE v.5.0; the therapy modifications described below are to be applied according to severity grading. If more than one type of AE occurs concurrently, the most severe grade will determine the modification. Each dose modification or treatment delay must be documented, including the respective reason. Re-escalation of selinexor is allowed as outlined in Table 3. If drug-related toxicity requires a treatment delay of more than 28 days, the patient will be taken off study treatment. For all  $\geq$  Grade 3 hematological or non-hematological AEs that are NOT selinexor related, after consultation with the Medical Monitor and at the discretion of the Investigator, selinexor dosing may be maintained.

Table 3 summarizes the study treatment dose levels; Table 4 describes supportive care and dose adjustment guidelines. General supportive care recommendations are provided below. Deviations from the guidelines are permitted after discussion between the PI and the treating physician.

In patients with renal impairment, start each drug at the following dose level:

- 1) Selinexor:
  - (a) CrCl  $\geq$ 15 mL/min: There are no dosage adjustments provided in the manufacturer's labeling.
  - (b) CrCl <15 mL/min: Patients with severe renal impairment are excluded from this study.
- 2) Clarithromycin:
  - (a) CrCl  $\geq$ 30 mL/minute: No dosage adjustment necessary.
  - (b) CrCl 15-29 mL/minute: Decrease clarithromycin dose by 50% by starting at dose level -1.
  - (c) CrCl <15: Patients with severe renal impairment are excluded from this study.
- 3) Pomalidomide:
  - (a) CrCl  $\geq$ 15 to <60 mL/minute: There are no dosage adjustments provided in the manufacturer's labeling. Compared to patients with normal renal function, pomalidomide pharmacokinetics were not significantly altered in patients with CrCl between 15 to 60 mL/minute.
  - (b) CrCl <15 mL/min: Patients with severe renal impairment are excluded from this study.
- 4) Dexamethasone:

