#### **7.7.2 Conditions Not Requiring Selinexor Dose Reduction**

The following conditions are exceptions to the dose-modification guidelines. Selinexor does not need to be held in the following cases:

- Alopecia of any grade
- Electrolyte or serum analyte (e.g., urate) abnormalities that are reversible with standard interventions. Treat hypokalemia and hypomagnesemia per institutional guidelines and repeat a 12-lead ECG to monitor the QTc as clinically indicated.

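### Three supportive-care instructions need correcting: selinexor at asymptomatic Grade 3 hyponatremia, the glucose unit for sodium correction, and unconditional day-1 aspirin

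*Combined protocol and SAP*

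**What the plan says.** **Hyponatremia (Table 4, section 7.7.1).** The Grade 2 row covers corrected sodium of Grade ≤ 3; from that number on, it reads "3 and continues to be asymptomatic, then patient may continue current dosing provided that intravenous saline and/or salt tablets (1-3 times daily) are provided". The Grade 3 or 4 row reads "Treat per institutional guidelines. Delay selinexor until sodium resolved to Grade" ≤ 1 (≥ 130 mmol/L), followed by a one-level selinexor reduction. It makes no exception for patients without symptoms.

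Three other texts bear on which row applies:
- Section 7.7.1: "the therapy modifications described below are to be applied according to severity grading".
- The closing sentence of Table 4: "All dose modifications should be based on the worst preceding toxicity".
- Section 7.7.2: "The following conditions are exceptions to the dose-modification guidelines. Selinexor does not need to be held in the following cases", one of which is "Electrolyte or serum analyte (e.g., urate) abnormalities that are reversible with standard interventions". It then names potassium and magnesium. It sets no grade limit and does not mention sodium.

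**Glucose trigger (Table 4).** The Grade 1 row says "Be certain that reported sodium level is corrected for concurrent hyperglycemia (serum glucose" > 150 mmol/L). The Grade 2 row carries this over: "Correct for hyperglycemia as outlined under Grade 1".

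**Thrombosis prophylaxis.** Section 7.8.7 gives aspirin 81 mg to patients at low VTE risk. Patients with multiple risk factors should have heparin, warfarin or another oral anticoagulant in place of aspirin. Section 7.8.13 lists daily aspirin 81 mg among the day-1 medications for the patient, with no risk condition and no reference to 7.8.7.

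**The concern.** Site staff work from dosing tables and day-1 lists, so the printed words matter even where the intent can be guessed.

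- **Hyponatremia.** For a patient with asymptomatic Grade 3 hyponatremia, one row of Table 4 can be read as allowing the current selinexor dose and the next orders a hold and a reduction. The event is foreseeable. Section 2.4.1.1 lists hyponatremia among the common (> 10%) Grade 3 or greater events with selinexor 80 mg twice weekly plus dexamethasone. Section 2.4.1.4 reports hyponatremia in 21% with once-weekly selinexor, pomalidomide and dexamethasone, grade not stated.
- **Glucose.** A trigger that no patient will reach means that sodium is not corrected during hyperglycemia, which weekly dexamethasone 40 mg makes likely.
- **Aspirin.** A day-1 list followed to the letter gives aspirin to patients for whom 7.8.7 specifies something else.

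At stake are consistent handling of the same event across the two sites named in the Protocol Summary, and the accuracy of hyponatremia grading.

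**Working it through.** **1. Hyponatremia rows side by side, for an asymptomatic patient**

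| Corrected sodium | Grade 2 row | Grade 3 or 4 row |
|---|---|---|
| Grade 2 | Continue, with saline or salt tablets | Does not apply |
| Grade 3 | Continue, if the printed limit is ≤ 3 | Delay to Grade ≤ 1, then one level lower |
| Grade 4 | Not covered | Delay to Grade ≤ 1, then one level lower |

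The conflict is confined to asymptomatic Grade 3. The sentence on applying modifications by severity grade and the worst-toxicity sentence both favour the Grade 3 or 4 row. The separate rule in 7.7.1 that the most severe grade decides covers different types of adverse event occurring together, so it does not settle this case. With < 3 in the Grade 2 row, the conflict disappears.

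**2. How often it could arise**

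The documents give no Grade ≥ 3 rate for this regimen and no asymptomatic share. The > 10% figure comes from 2 × 80 = 160 mg of selinexor a week. Here it is 3 × 60 = 180 mg per 28 days, or 180/4 = 45 mg a week, about 28% of that. The rates below are therefore assumptions.

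Expected cases = 26p; chance of at least one = 1 − (1 − p)^26.

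- p = 5%: 26 × 0.05 = 1.3; 1 − 0.95^26 = 74%
- p = 10%: 26 × 0.10 = 2.6; 1 − 0.90^26 = 94%
- p = 15%: 26 × 0.15 = 3.9; 1 − 0.85^26 = 99%

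These count every Grade ≥ 3 event, including symptomatic and Grade 4 events on which the rows agree. They are upper bounds. If the Grade ≥ 3 rate is 5% and half of those events are asymptomatic Grade 3 (assumption), p = 2.5%: 26 × 0.025 = 0.65 expected; 1 − 0.975^26 = about 48%.

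**3. Glucose unit**

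The plan states its figure (> 150 mmol/L) without deriving it. Taking the molar mass of glucose as 180.16 g/mol (assumption), mg/dL = mmol/L × 18.016.

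- 150 mmol/L × 18.016 = 2,702 mg/dL
- 150 mg/dL ÷ 18.016 = 8.3 mmol/L

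Glucose of 200, 300, 400 and 600 mg/dL is 11.1, 16.7, 22.2 and 33.3 mmol/L. All four fall below the printed trigger and all four exceed 150 mg/dL.

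Direction: uncorrected sodium reads low during hyperglycemia. Assuming a correction of 1.6 to 2.4 mmol/L sodium per 100 mg/dL of glucose above 100, the amount missed at 300 mg/dL is 2 × 1.6 = 3.2 to 2 × 2.4 = 4.8 mmol/L. That can raise the recorded grade.

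**4. Aspirin**

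- Low VTE risk: 7.8.7 and 7.8.13 agree.
- Multiple risk factors: 7.8.7 gives an anticoagulant in place of aspirin; 7.8.13 gives aspirin. The only exception clause in 7.8.13 concerns study-drug reduction for renal or hepatic impairment.
- Such patients can enroll. Exclusion 18 removes only VTE within 6 months and known inherited thrombophilia. Obesity and older VTE are not excluded, erythropoietin is acceptable (exclusion 8a), and creatinine clearance down to 15 mL/min is allowed (exclusion 6), while 7.8.7 counts eGFR below 30 mL/min as a risk factor.

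The documents give no share of patients with multiple risk factors, so no count follows.

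**The case against.** **Hyponatremia.** The point rests on one character in a table whose extracted text is visibly shifted: nausea text appears beside the hyponatremia label. That the same table prints < correctly for hemoglobin below 8 g/dL shows only that the sign can survive extraction, not that it did so here. Even with ≤, the sentence sits inside the Grade 2 row, and Grade 3 patients have their own explicit row. Correcting for glucose raises sodium, so a reported Grade 2 cannot become Grade 3 through correction. Much of this stands: it lowers confidence and shows the probable intent. It does not remove the permission, because the same row goes on to discuss Grade 2 that worsens.

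**Section 7.7.2.** A reader might infer that it creates a further regimen allowing selinexor at any sodium grade. The text does not support that. It is a general, permissive exception that goes on to name potassium and magnesium, and the specific hyponatremia rows are the natural authority. A clarifying sentence there is optional.

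**Glucose.** The operative instruction is to correct for hyperglycemia; the number is parenthetical and implausible on sight. That reduces the practical effect but leaves the unit wrong.

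**Aspirin.** Section 7.8.7 is the dedicated section. The day-1 list also omits other conditions, such as the allergy alternative to trimethoprim-sulfamethoxazole in 7.8.3. A careful investigator would probably follow 7.8.7, and exclusion 19 means that enrolled patients can take an anticoagulant. Aspirin alone, or aspirin plus an anticoagulant, is a possible literal result, not a predicted one.

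**Overall.** Deviations from the guidelines are allowed after discussion with the PI (7.7.1). This limits harm but does not make the texts agree.

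**Conclusion.** Wrong as written on all three counts, with medium confidence on hyponatremia (it depends on ≤ being in the source PDF) and high confidence on the glucose unit and the aspirin line. These are wording corrections worth making.

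Three stronger readings should be resisted:
- **That the trial is very likely to meet the hyponatremia conflict.** The 74% to 99% figures are upper bounds at assumed Grade ≥ 3 rates of 5% to 15%. The relevant chance is lower, about 48% under the assumptions of a 5% rate and a half share, and the documents do not fix it.
- **That the glucose error leads to unsafe dosing.** Its literal effect runs the other way: over-graded hyponatremia and needless selinexor holds.
- **That the efficacy conclusion is at risk.** None of the three instructions enters the Simon stopping and rejection rules or the response-rate analysis in section 12. Dose lost under a hold-and-reduce rule would be the cost of the rule that was probably intended, not a measure of harm from the error.

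**What to change.** 1. **Table 4, hyponatremia, Grade 2 row.** Check the source PDF. If ≤ 3 is printed, change it to < 3. Optionally add to 7.7.2 that the reversible-electrolyte exception does not override the Grade 3 or 4 hyponatremia row.
2. **Table 4, hyponatremia, Grade 1 row.** Change the trigger to serum glucose > 150 mg/dL (about 8.3 mmol/L), confirmed by the clinical team. The Grade 2 row then inherits the correct value.
3. **Section 7.8.13.** Replace the aspirin line with: aspirin 81 mg daily or anticoagulant per VTE risk, see 7.8.7.

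The cost is a wording amendment, which needs IRB approval before use (Statement of Compliance; 11.2.1). Sample size, stopping rule and analysis do not change.
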